#### **4.1.1 Main study parameter/endpoint**

Our primary outcome will be patient-reported health-related quality of life *and* patient experience of care, in line with the 2 patient-related aims of the Quadruple Aims. Patient-reported health-related quality of life will be measured using the PROMIS global 10 questionnaire and the patient experience of care will be measured using the P3CEQ questionnaire. These questionnaires have been chosen after piloting several questionnaires

in the preceding phase. Patients experienced these questionnaires as easy to fill in and to understand and both questionnaires match well with the concepts we want to measure.

The PROMIS global 10 assesses a person's health-related quality of life. Two dimensions representing physical and mental health underlie the global health items in PROMIS. These global health scales can be used to efficiently summarize physical and mental health in patient-reported outcome studies, Global Physical Health (GPH; 4 items on overall physical health, physical function, pain, and fatigue) and Global Mental Health (GMH; 4 items on quality of life, mental health, satisfaction with social activities, and emotional problems).[12] The 10 global health items include ratings of the five core PROMIS domains with a response scale ranging from 1 to 5, the labels of those scores different per question, but a higher scoring is always indicating a better health-related quality of life. The PROMIS global 10 is publicly available and has been widely used as outcome measure for quality of life in studies on different diseases.

The Person-Centred Coordinated Care Experience Questionnaire (P3CEQ) is a brief questionnaire that meets the requirements for a PREM that could assess the quality of care and guide quality improvement for people with (multiple) chronic conditions. It has been specifically designed to assess the experience of person-centred coordinated care, informed by a theoretical model that was developed to consider the relationship between care coordination, continuity and person-centred care. The P3CEQ was originally developed in the United Kingdom for persons with chronic conditions using primary care services.[13] Recently it has been translated and validated for the Dutch population.[14] It contains 14 items and the response scale ranges from 'never' (0), 'sometimes' (1), 'often' (2) and 'always' (3).

Because we value each aim (population health and patient experience) as equally important, we are using a composite primary outcome, which consists of the percentage of patients who have a clinically relevant improvement of at least the minimal clinically important difference (MCID), defined as  $0.5 \times \text{SD}$  of the baseline mean, in either the PROMIS GMH score OR the PROMIS GPH score OR the P3CEQ-score AND who experience no decrease of at least the MCID in either the PROMIS GMH score OR the PROMIS GPH score OR the P3CEQ-score.

[figure not shown]
#### **4.1.2 Secondary study parameters/endpoints (if applicable)**

- PROMIS dimension GPH score
- PROMIS dimension GPM score
- P3CEQ-score

- Patient Activation Measure (PAM)
- EQ-5D-5L
- Health care use according to Medical Consumption Questionnaire
- Health care use according to general practice data
- Body weight, BMI, smoking status, HbA1c, glucose, cholesterol levels and blood pressure from general practice data (registered for normal care).
- Experience of healthcare providers on COPILOT and MAS-GZ questionnaire

#### 4.2 Randomisation, blinding and treatment allocation

The unit of randomisation will be the general practice (cluster). Practices will be randomised to intervention group (10 clusters) or comparator (5 clusters) in a 2:1 ratio. Five additional clusters will be randomised to the control group by a 2:1 ratio randomisation procedure in the parallel cluster RCT named EMBOSS in which the GDM programme will be adjusted to the needs of patients with low socioeconomic status (SES). In the EMBOSS cluster RCT the adjusted intervention will be provided to patients with low SES and at 12 months follow-up the effects will be compared to patients with low SES who have received care as usual. Figure 2 illustrates the combined randomisation procedure of both the OPTIMA FORMA and the EMBOSS cluster RCT.

**Figure 2. Randomisation procedures in the OPTIMA FORMA and EMBOSS cluster RCTs**

After practices have been recruited, the practices will be randomised to the intervention or the usual care group. To avoid an imbalance between the randomised groups stratification will take place according to (i) the primary care cooperative, and (ii) the socioeconomic status of the practice population. Because of the nature of the intervention, it will not be possible to mask intervention allocation from the GPs or the patients. The research nurses who will collect the outcome data and the researchers who will perform the analyses will be blinded to treatment allocation.

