## 2. STUDY DESIGN

We will perform a cluster randomized controlled trial with a follow-up time of 12 months.

The three participating primary care cooperatives, i.e. Nijmegen, Arnhem, and Doetinchem, will recruit 15 general practices (clusters) who will be randomized using a 2:1 ratio in two study groups:

1. The intervention group: the GDM programme including a person-centered, integrated, and holistic approach
2. The control group: care as usual according the current SDM programmes

All practices will receive instructions from the research team on the procedures of the evaluation study. Participating practices will then start recruiting patients from a random sample of eligible patients, i.e. patients with DM2, COPD, or CVD who are currently receiving SDM. After written informed consent, information will be collected through questionnaires at baseline, 6 months and 12 months, and by interviews and data collection from electronic medical records. Information will also be collected from the participating healthcare providers through questionnaires and interviews.

In the two months prior to the start of the intervention, all practices in the intervention group will be trained in providing GDM by their own primary care cooperative. During follow-up two to three intervention meetings will take place including peer coaching and case study discussions.

Practices who are allocated to the usual care group will not receive any training, but will continue with their SDM programmes.

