Because we value each aim (population health and patient experience) as equally important, we are using a composite primary outcome, which consist of the percentage of patients who have a clinically relevant improvement of at least the minimal clinically important difference (MCID), defined as  $0.5 \times \text{SD}$  of the baseline mean, in either the PROMIS GMH score OR the PROMIS GPH score OR the P3CEQ-score AND who experience no decrease of at least the MCID in either the PROMIS GMH score OR the PROMIS GPH score OR the P3CEQ-score.

In our recent pilot study [unpublished] we followed 98 patients who received our intervention for six months. Of the 79 patients who completed all questionnaires, we found that in 30.4% of the patients the requirements for a positive score on the composite primary outcome were met. Loss to follow-up was 20%. Based on these results and the longer duration of intervention in the evaluation study (12 months vs 6 months), we hypothesised that in the evaluation study 35% of the intervention patients compared to 20% of the usual care patients will improve more than  $0.5 \times$  the expected SD of baseline mean on one of the scores at 12 months, and show no decrease of the MCID on the other scores. We estimate that we need a total sample size of 680 patients (17 practices with an average of 40 patients per practice) to detect a difference of 15% between the control and intervention group, taken into account an alpha level of 5%, a power of 80%, an intra-class correlation coefficient (ICC) of 0.03 [15], and a loss to follow-up of 20%.

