### 6. STATISTICAL ANALYSIS

Data analysis will be performed according to the intention-to-treat principle. Data from patients who discontinued follow-up will be included in the analysis up to the point of dropout. Descriptive analyses will be performed to describe the patient characteristics. Mean and standard deviation (std) or median and interquartile range for continuous characteristics and number and percentages for categorical characteristics will be determined. The relationship between treatment and outcome measures measured at 6 and 12 month follow up will be analysed with mixed three level linear or logistic regression, taking into account that the times of measurement (after 6 and 12 months) are clustered within patients, and patients within general practices. We will perform a

model with a random intercept and all other variables fixed. To test the effect of the intervention a model with time, group (intervention or control) and the interaction between time and group will be performed. Covariates included in the analyses will be age, sex, smoking status, education level, and social support. A value of  $p < 0.05$  will be considered statistically significant for all analyses, based on two-sided testing. Analyses will be performed using the Statistical Package for Social Sciences (SPSS, IBM Corp., Armonk, NY) version 25.

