### **6.1 Primary study parameter(s)**

Our primary outcome is a dichotomous composite score ( yes / no MCID improvement in health-related quality of life or quality of healthcare), which is based on the scores of PROMIS dimensions (GPH, GPM) and the P3CEQ-score.

To test the effect of the intervention over time, we use a three level multilevel logistic model. A model with time , group (intervention or control) and the interaction between time and group will be performed. With this model we can test the effect of the intervention during the entire study period and the intervention effects at 6 months and at 12 months.

In a mixed model both fixed and random effects can be analyzed. We perform a model with random effect for practice and patients. All other variables will be held fixed. Covariates included in the analyses will be age, sex, smoking status, education level, and social support.

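### Randomisation is stratified by cooperative and practice SES but no model includes either factor, and Section 2.4 does not give the power of the design to be analysed (10:5, or 10:10 with the EMBOSS controls)

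*Combined protocol and SAP*

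**What the plan says.** **Randomisation.** Under Figure 2 in Section 4.2, the plan states that "stratification will take place according to (i) the primary care cooperative, and (ii) the socioeconomic status of the practice population", in order to avoid imbalance between the groups.

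**Models.** Section 6.1 specifies: "A model with time , group (intervention or control) and the interaction between time and group will be performed". Random effects are practice and patient. Sections 6, 6.1 and 6.2 each repeat the same list: "Covariates included in the analyses will be age, sex, smoking status, education level, and social support". Cooperative and practice SES appear in none of them.

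**Size and allocation.** Section 2.4 asks for "a total sample size of 680 patients (17 practices with an average of 40 patients per practice") and gives no allocation ratio. Section 2 says that the cooperatives "will recruit 15 general practices (clusters) who will be randomized using a 2:1 ratio in two study groups", and Section 4.2 that "Practices will be randomised to intervention group (10 clusters) or comparator (5 clusters) in a 2:1 ratio".

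**EMBOSS.** Section 4.2 continues: "Five additional clusters will be randomised to the control group by a 2:1 ratio randomisation procedure in the parallel cluster RCT named EMBOSS". It describes the comparison within EMBOSS as one in which "the effects will be compared to patients with low SES who have received care as usual". Sections 2.4 and 6 to 6.2 do not mention EMBOSS. Section 4.7 ties termination of the current design to failure to recruit the necessary number of clusters, without giving that number.

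**The concern.** A factor used to restrict randomisation normally belongs in the analysis model. Stratifying makes the arms more alike on that factor. A model without the factor leaves its variance in the between-practice term, so the standard error does not describe the design that was run. With 15 to 20 practices, between-practice variance dominates precision, so the choice can matter. The terms already planned do not fill the gap. Education level is a patient characteristic, not the SES stratum of the practice, and a random practice intercept absorbs between-practice variance without separating the part that the strata explain.

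On power, Section 2.4 describes neither 15 practices at 10:5 nor 20 at 10:10. Which of these is the primary comparison decides whether the 80% is reached. It also decides what number Section 4.7 should be judged against, since 17 are calculated, 15 are recruited here and 5 more come from EMBOSS.

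**Working it through.** **Inputs.** Section 2.4: response 35% versus 20%, alpha 5%, power 80%, ICC 0.03, 40 patients per practice, 20% loss. Section 6: two-sided tests. Completers per practice: 40 × 0.8 = 32. Design effect: 1 + (32 − 1) × 0.03 = 1.93.

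**1. Reproducing the plan's figure**

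- *Equal arms, pooled:* n = [1.96 √(2 × 0.275 × 0.725) + 0.842 √(0.20 × 0.80 + 0.35 × 0.65)]² / 0.15² = 138 per arm. Then 276 × 1.93 / 0.8 = 666 patients, or 16.6 practices, rounded up to 17 practices and 680 patients. Power with 17 practices in equal arms is 81%.
- *2:1, unpooled:* control n = (1.96 + 0.842)² × (0.16 + 0.2275/2) / 0.15² = 95.5. Then 3 × 95.5 × 1.93 / 0.8 = 691 patients, or 17.3 practices. Seventeen practices split 11:6 give 80.1% unpooled (76.4% pooled).
- *2:1, pooled:* 106 + 212 = 318. Then 318 × 1.93 / 0.8 = 767 patients, or 19.2 practices. This does not fit 680.

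The stated figure is therefore reproduced by equal arms and, approximately, by an unpooled 2:1 calculation.

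**2. Fifteen practices at 10:5**

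Effective n: 10 × 32 / 1.93 = 165.8 and 5 × 32 / 1.93 = 82.9.

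- Unpooled SE = √(0.2275/165.8 + 0.16/82.9) = 0.0575. Power = Φ(0.15/0.0575 − 1.96) = 74%.
- Pooled: mean response 0.30, null SE = √(0.21 × (1/165.8 + 1/82.9)) = 0.0616. Power = Φ((0.15 − 1.96 × 0.0616)/0.0575) = 69%.
- Noncentral t on 15 − 2 = 13 df: 67.5%.

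All three are below 80%. The result is sensitive to the ICC: pooled power would be 85.7% at an assumed 0.01 and 56.7% at an assumed 0.05. The plan uses 0.03.

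**3. Twenty practices at 10:10**

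Effective n is 165.8 per arm. Power is 86.7% pooled, 87.3% unpooled and 83.5% by t on 18 df. This assumes that each EMBOSS control practice supplies 40 eligible patients with the same 20% response.

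**4. Omitting or including the strata**

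The plan does not say how much between-practice variance the two factors explain, so shares of 0%, 25% and 50% are assumed. Simulation settings: 8,000 trials per cell, practice-level regression with an equal-variance t test, 32 completers per practice, ICC 0.03, three cooperatives by two SES levels (two levels assumed), and permuted blocks within strata. Each cell shows the result without / with the strata in the model.

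| Share explained | Type I error, 10:10 | Power, 10:10 | Power, 10:5 |
|---|---|---|---|
| 0% | 5.0% / 5.0% | 83.1% / 81.0% | 62.8% / 58.4% |
| 25% | 3.8% / 5.1% | 84.1% / 85.8% | 63.3% / 64.9% |
| 50% | 2.8% / 5.0% | 84.4% / 90.0% | 62.7% / 71.6% |

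Simulated power at 10:5 lies below 67.5% because the equal-variance t test overstates the variance of the smaller arm.

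With a normal (1.96) reference instead of t, repeat simulations without the strata at 10:10 gave type I error of 6.0% to 6.4%, 5.2% to 5.5% and 3.8% to 4.7% at the three shares. The direction of the departure from 5% therefore depends on the reference distribution, which the plan does not name.

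**The case against.** The strongest reply is that nothing is underpowered. Section 4.2 says that the additional clusters go to the control group and refers to a combined randomisation procedure. The natural reading is 10 versus 5 + 5, which exceeds both the 80% and the 17 practices of Section 2.4. On that reading 15, 17 and 5 are not rival counts, and what is missing is a sentence. Figure 2 is not shown in the copy reviewed and may settle how the practices were drawn. This largely stands. A reader might infer from 69% that the trial is underpowered, but that holds only if the EMBOSS controls are left out, which is the less likely reading.

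A reader might also infer that Section 2.4 assumed equal arms and so contradicts the 2:1 design. The documents do not support that: no ratio is given, and an unpooled 2:1 calculation comes close to the same total.

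A third tempting inference is that leaving out the strata makes the test conservative. That holds for a practice-level t test when the factors predict response. The plan specifies a three-level logistic model with patient covariates and names no degrees-of-freedom method; with a normal reference the error can exceed 5%.

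Finally, the gain from adding the strata rests on assumed variance shares, and at a share of zero there is a loss. That also stands. The case for adding them is that the analysis should follow the randomisation at a small known cost, not that a gain is assured.

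**Conclusion.** Two points hold.

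First, both stratification factors are absent from every stated model. This causes no bias in the group effect. It loses precision to the extent that the factors predict response, and the nominal error rate does not reflect the stratified design. The size and direction of the type I effect cannot be fixed from the plan.

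Second, the 80% in Section 2.4 is not what 15 practices at 10:5 deliver at the plan's inputs: 67.5% to 74%, depending on the test. With the EMBOSS controls, 10:10 delivers 83.5% to 87%, subject to the assumptions on patient numbers and control rate above. Section 2.2 sets no SES limit, but EMBOSS makes its own comparison in low-SES patients, so which patients those five practices would contribute needs to be stated. The plan does not show that the EMBOSS controls bias the comparison, and no such claim is made here.

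Both points should be settled before analysis. Neither invalidates the trial.

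**What to change.** 1. **Sections 6, 6.1 and 6.2:** add cooperative and practice-SES stratum as fixed effects, and name the reference distribution for the group test.
2. **Section 2.4:** state the allocation ratio and restate the power for the design actually analysed, both 10:10 with the EMBOSS controls and 10:5 without. Use the same practice count in Section 4.7.
3. **Sections 4.2 and 6:** if it is intended, state that the five EMBOSS control practices enter the primary analysis, with patients selected by the Section 2.2 criteria and the Section 2 random sample, not only low-SES patients.
4. **Sensitivity analysis:** 10 versus 5 within OPTIMA FORMA, with its lower power stated. If the EMBOSS controls were drawn in a separate randomisation, this comparison is also the check on trial of origin.

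**Cost.** Wording, two model terms and one sensitivity analysis; no added practices, patients or visits. Three cooperatives and two assumed SES levels use 2 + 1 = 3 practice-level df. By df alone, t-based power falls from 83.5% to 82.6% at 10:10 and from 67.5% to 65.4% at 10:5. With the imperfect balance of small strata, and if the factors explain nothing, the simulated loss is about 2 points at 10:10 (83.1% to 81.0%) and about 4 at 10:5 (62.8% to 58.4%). In the simulation it becomes a gain at an assumed share of 25%.

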### 4.3 Study procedures

#### Population health

Category	Measurement instrument	Time
Health related quality of life	EQ-5D-5L	Baseline, 6, 12 months
Self-management	Patient Activation Measure (PAM)	Baseline, 6, 12 months
Health related quality of life	PROMIS GLOBAL-10	Baseline, 6, 12 months
Unscheduled healthcare	Data from medical records	12 months
Physiological parameters	Data from medical records	12 months

#### Patient experience

Category	Measurement instrument	Time
Person-centredness of care	Person Centred Coordinated Care Experiences Questionnaire (P3CEQ)	Baseline, 6, 12 months
Experiences	Focus-group interviews	12 months

#### Healthcare provider experience

Category	Measurement instrument	Time
Positive affect	CO-PILOT questionnaire MAS-GZ questionnaire	Baseline, 6, 12 months
Experiences	Focus-group interviews	12 months
Competences	Focus-group interviews Appropriate questionnaire	12 months At baseline and 12 months

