**Intervention:** a GDM programme including person-centered and holistic care. This programme will replace the SDM programmes for DM2, COPD and CVD that are currently used in the participating primary care cooperatives.

**Main study parameters/endpoints:** effectiveness will be evaluated by Quadruple Aim outcomes at baseline, at 6 months, and at 12 months follow-up by comparing changes in the intervention group with the comparator group. Patient experiences will be measured with the P3CEQ questionnaire. Population health will be measured with the PROMIS Global-10 questionnaire. Self-management will be measured with the Patient Activation Measure (PAM) score. Healthcare professional experiences will be measured with the MASGZ and the COPILOT questionnaire. Data for calculating costs and conducting a cost-effectiveness analyses will be measured by the Medical Consumption questionnaire and the EQ-5D questionnaire and by process outcomes such as the number and type of consultations and referrals, and duration of consultations from the Electronical Medical Files. At 12 months, a purposive sample of patients and professionals will participate in focus group interviews to collect information on experiences and facilitators and barriers for further implementation. Also, the competences needed by the healthcare professionals to provide personalised and integrated chronic care will be explored.

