### 3. TREATMENT OF SUBJECTS

#### 3.1 OPTIMA FORMA intervention

The core of GDM programme including person-centered and holistic approach is a cyclical process described in Figure 1. The practice nurse in the general practice will act as case manager. She/he can consult the general practitioner or other health providers when necessary. The first step in the intervention is assessing the integral health status of the patient (health across multiple domains, including physiological measurements and symptoms of disease), using a (preferably digital) questionnaire at home and physical measurements. The second step is an appointment in which the results are discussed with the patient in a semi-structured way. The case manager discusses if the results are recognizable, if there are other issues which haven't come up, and the priorities of the patient. Personal goals are formulated in the third step, which can range from purely medical goals to social goals. In the fourth step, the healthcare professional and patient will choose through shared-decision making the most appropriate interventions and support to achieve these goals. The goals and interventions are documented in a personal healthcare plan, which is preferably digitally available for all relevant healthcare professionals and the patient. Next, referrals are made if necessary and the treatment is started. An evaluation is planned and carried out, if necessary multiple times. If a treatment goal is reached or another treatment goal is more urgent, the cycle can be repeated.

[figure not shown]

Figure 1. Presentation of the cyclic process of the GDM programme

In order to provide the OPTIMA FORMA intervention to participating patients all healthcare professionals involved will be trained by their primary care cooperative on the concept of Positive Health, communication skills, use of materials and ICT, and interprofessional collaboration prior to the start of the intervention. During follow-up, the

practices will receive additional support from the primary care cooperative through intervision meetings and case report discussions.

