### **6.2 Secondary study parameter(s)**

The relationship between treatment and secondary outcome measures measured at 6 and 12 month follow up will be analysed with mixed three level linear or logistic regression, taking into account that the times of measurement (after 6 and 12 months) are clustered within patients, and patients within general practices. A model with time, group (intervention or control) and the interaction between time and group will be performed. Covariates included in the analyses will be age, sex, smoking status, education level, and social support

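### Provider experience has no fitting analysis model in Section 6.2, and its baseline is not dated against training that only intervention practices receive

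*Combined protocol and SAP*

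**What the plan says.** **Endpoint and schedule.** Section 4.1.2 lists provider experience on COPILOT and MAS-GZ among the secondary endpoints. The provider table in Section 4.3 schedules it as "CO-PILOT questionnaire MAS-GZ questionnaire Baseline, 6, 12 months". The competences row of the same table has an unnamed questionnaire "At baseline and 12 months", with no 6-month wave. Competences are not in the Section 4.1.2 list; the Summary describes them as something to be explored.

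**Timing.** Section 2 gives no date for the provider questionnaires: "Information will also be collected from the participating healthcare providers through questionnaires and interviews". The same section states: "In the two months prior to the start of the intervention, all practices in the intervention group will be trained in providing GDM". For the control arm it states: "Practices who are allocated to the usual care group will not receive any training". Section 3.1 describes the training as being "on the concept of Positive Health, communication skills, use of materials and ICT, and interprofessional collaboration prior to the start of the intervention".

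**Analysis.** The Summary says effectiveness will be judged "by comparing changes in the intervention group with the comparator group". Section 6.2 prescribes for secondary outcomes a three-level model: measurement times at 6 and 12 months, within patients, within practices, with time, group and their interaction. It adds: "Covariates included in the analyses will be age, sex, smoking status, education level, and social support". No baseline score is among the covariates.

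**The concern.** Provider experience is one of the four aims that the trial sets out to evaluate, and two things about its analysis are unsettled.

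First, the stated model has no provider in it. Its middle level is the patient, and two of its covariates, smoking status and social support, are patient characteristics that no section plans to collect from providers. The analyst would have to decide what to substitute. The model also leaves out the provider's own baseline score, although that score is collected.

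Second, the training is aimed directly at providers and covers matters that provider-experience and competence questionnaires could plausibly pick up. It takes place before the intervention starts, in one arm only. If the provider baseline were taken at the start of follow-up, it would already contain part of the effect in the intervention arm and none in the control arm. A pre-training score cannot be recovered afterwards, so the order has to be fixed in advance.

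**Working it through.** The plan gives no sample size, number of providers or expected effect for provider outcomes. Its only calculated figure, 680 patients, concerns the patient-level primary outcome and is not in question here. The check is therefore mainly a comparison of sections.

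**1. Does the Section 6.2 model fit COPILOT and MAS-GZ?**

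| Feature | Section 6.2 | Provider data |
|---|---|---|
| Lowest level | 6 and 12 months | 6 and 12 months (baseline also collected) |
| Middle level | patient | provider |
| Top level | practice | practice |
| Age, sex, education level | included | could apply, but collection from providers is not described |
| Smoking status, social support | included | collection from providers is not described |
| Baseline score | not included | collected |

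The lowest and top levels carry over. The middle level and part of the covariate list do not.

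**2. Is the provider baseline dated?** For patients, Section 7.2 fixes an order: the baseline questionnaire is completed, and then the practice is told that this patient can start the new care. Sections 2 and 4.3 contain no corresponding rule for providers. The documents allow a provider baseline before, during or after the two months of training.

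**3. What would a post-training baseline do?** Let D be the true between-arm difference at 6 or 12 months, T the between-arm difference that training has already produced at baseline, and b the within-arm slope of the follow-up score on the baseline score.

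| Contrast | Baseline before training | Baseline after training |
|---|---|---|
| Follow-up score only | D | D |
| Change from baseline | D | D − T |
| Follow-up adjusted for baseline | D | D − bT |

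With s = T/D, the change contrast is D × (1 − s). It equals D at s = 0 and zero at s = 1, and it reverses sign if s exceeds 1, that is, if the effect of training fades later. Nothing in the documents gives T, D or b, so no value can be put on the bias.

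Section 6.2 as written, with 6 and 12 months as the occasions and no baseline term, corresponds to the first row. The Summary's comparison of changes corresponds to the second. The plan does not say which applies to provider outcomes.

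**4. Precision, on assumed values.** Assume m = 1 to 4 providers per practice, a provider ICC ρ of 0.03 to 0.30, two-sided 5%, 80% power, a normal approximation and no baseline adjustment. With a intervention and c control practices, the detectable difference in SD units is

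(1.96 + 0.84) × √{[1 + (m − 1)ρ] × [1/(am) + 1/(cm)]}

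- 10 versus 5 practices, m = 4, ρ = 0.03: 2.80 × √(1.09 × 0.075) = 0.80
- 10 versus 5 practices, m = 1: 2.80 × √0.30 = 1.53
- 10 versus 10 practices, m = 4, ρ = 0.03: 2.80 × √(1.09 × 0.05) = 0.65
- 10 versus 10 practices, m = 1: 2.80 × √0.20 = 1.25

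The second pair counts the five extra control clusters from the parallel trial (Section 4.2); the plan does not say whether their providers will be surveyed. On these assumptions only large differences are detectable. That is a reason to use the baseline score, and therefore to make sure it is taken before training.

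**The case against.** The strongest reply is that no error of timing has been shown. The documents are silent, and the one order they do give, for patients, puts baseline before the new care. A reader might infer that the provider baseline follows training and that the comparison is therefore biased towards no effect. The documents do not support that: they never place the provider baseline after training, and the direction of any bias would depend on how training moves the scores. This objection stands, and the timing point is conditional.

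A second reply is that the 6- and 12-month contrasts in Section 6.2 do not subtract baseline, so a late baseline would not affect them. That also stands. It is why one cannot say that this aim is inestimable: a follow-up comparison between randomised practices remains valid. The Summary, however, announces a comparison of changes. Adjusting for baseline, which is the better analysis, would also make the timing matter.

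Third, a reader might infer that the model cannot be fitted at all, or that the analysis will necessarily be devised after the data are seen. Neither follows. Reading provider for patient gives a workable structure, and age, sex and education level can describe providers. The absence of a plan to collect social support from providers proves little by itself, since its collection from patients is not described either. What remains is that the plan does not make the substitution, choose the covariates or use the baseline score.

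Fourth, a reader might extend the model criticism to competences. They are not a listed secondary endpoint, so Section 6.2 does not reach them. Only the baseline timing applies to them.

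**Conclusion.** The point holds in two parts of different strength. For COPILOT and MAS-GZ, the only model stated for secondary outcomes does not describe provider data as written and leaves out a baseline score that is already collected; this follows directly from Sections 4.1.2, 4.3 and 6.2. The baseline timing is a gap with a conditional consequence. If the provider questionnaires were completed after training, a comparison of changes would lose the whole of the effect present by then, and a baseline-adjusted comparison would lose a fraction of it. An unadjusted comparison at follow-up would lose nothing.

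No size can be given for that bias from the documents. The detectable differences of roughly 0.65 to 1.5 SD rest on assumed provider numbers and ICCs and show only that the endpoint has little precision to spare. The matter concerns one secondary endpoint and, for timing alone, the exploratory competences questionnaire. The primary analysis is not affected.

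**What to change.** **Section 4.3.** State that the provider baseline questionnaires (COPILOT, MAS-GZ and the competences questionnaire) are completed before the first training session, preferably before allocation is disclosed to the practice, and in the same calendar window in control practices. Count 6 and 12 months from one reference date defined the same way in both arms. The start of the new care will not serve, because control practices start nothing new.

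**Section 6.2.** Specify for COPILOT and MAS-GZ a model of occasions (6 and 12 months) within provider within practice, with time, group and their interaction, adjusted for the provider's baseline score and without smoking status and social support. The two changes belong together, since baseline adjustment is safe only if the baseline precedes training.

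**Cost.** A few sentences in two sections and no additional questionnaires. The downside is that practices must supply provider contact details somewhat earlier.
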